### Sensitivity Analysis of PFS

Sensitivity analyses of PFS will be based on the Full Analysis Set using censoring rules from [Table 2](#), along with the following exceptions listed below:

Sensitivity Analysis 1: In this analysis, baseline tumor removal before or after completion of the Week 18 tumor assessment will be evaluated as part of the study drug therapy and will not be considered as a new anticancer therapy (see difference in [Table 2, rule 4](#)).

Sensitivity Analysis 2 ([EMA guidance \[Reference 11\]](#)): In this analysis, PD or death after two or more missing assessments, or after receiving a new anticancer therapy will be considered as a PFS event (see differences in [Table 2, rules 4 and 7](#)). The removal of baseline lesion(s) before or after completion of the Week 18 tumor assessment will be considered as a new anticancer therapy.

## 6.4.2 Secondary Efficacy Analyses

### 6.4.2.1 PFS-4m and PFS-1y Rate by IIR

The PFS-4m rate and PFS-1y rate per IIR will be estimated using the K-M method for the primary efficacy endpoint PFS per IIR. PFS-4m/PFS-1y rate and their Greenwood standard errors will be evaluated using the K-M estimates from both treatment groups. The statistical significance of the difference in the 2 K-M PFS-4m/PFS-1y rates will be based on the 2-sided 95% CI. This 2-sided 95% CI and a p-value will be constructed using the difference of these 2 K-M PFS-4m/PFS-1y rates and the 2 corresponding Greenwood standard errors.

### 6.4.2.2 Overall Survival

Overall survival is defined as the time from the date of randomization to the date of death. All deaths during the study will be considered as OS events.

Subjects who were lost to follow-up or who withdrew consent will be censored at the date the subject was last known to be alive. Subjects who are still alive at the data cut-off date will be censored at the data cut-off date.

Determination of date of OS event or censoring is summarized in Table 3 below.

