#### 4.2.2.2 Follow-up Period

The Follow-up Period begins the day after the Off-Treatment Visit and will continue for up to 2 years after end of treatment for a subject, unless the subject withdraws consent, or is lost to follow-up, or the sponsor terminates the study.

Subjects may at any time withdraw consent for further study participation. No further data will be collected on subjects once consent has been withdrawn; however, an investigator may consult public records to establish survival status if permitted by local regulations.

All adverse events (AEs), including serious adverse events (SAEs), will be captured for 30 days after the last dose of study drug.

All subjects who end study treatment without IIR confirmed PD will continue to undergo tumor assessments every 6 weeks until Week 18, then every 9 weeks until Week 54, thereafter, every 12 weeks until IIR confirmation of radiographic evidence of PD as described in the tumor assessments in the assessment schedule, or until another anticancer therapy is initiated.

Subjects in both Arm A and Arm B will be followed for survival every 12 weeks ( $\pm 1$  week) and all subsequent anticancer treatments received will be recorded. Subjects who are being

followed for survival at the primary analysis (ie, at the end of the Randomization Phase) will continue to be followed for survival during the Follow-up Period of the Extension Phase.

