### 6.1.2 Secondary Endpoints

1. Progression-free survival rate at 4 months (PFS-4m) by IIR is defined as the percentage of subjects who are alive and without PD at 4 months from the randomization date as determined by IIR of radiological imaging using RECIST 1.1. The PFS-4m rate is estimated using the Kaplan-Meier (K-M) method.
2. Progression-free survival rate at 1 year (PFS-1y rate) by IIR is defined as the percentage of subjects who are alive and without PD at 1 year from the randomization date as determined by IIR of radiological imaging using RECIST 1.1. The PFS-1y rate is estimated using the K-M method.
3. Overall survival (OS) is defined as the time from the date of randomization to the date of death from any cause. Subjects who are lost to follow-up and those who are alive at the date of data cutoff for the primary analysis, will be censored at the date the subject was last known to be alive, or date of data cutoff for the primary analysis, whichever occurs first. Overall survival rate at 1 year (OS-1y) will be estimated using the K-M method.
4. Objective response rate by IIR at 4 months (ORR-4m) is defined as the proportion of subjects who have best overall response of complete response (CR) or partial response (PR) as determined by IIR using RECIST 1.1 within the first 4 months.
5. Objective response rate (ORR) by IIR is defined as the proportion of subjects who have best overall response of CR or PR as determined by IIR using RECIST 1.1.
6. Safety will be assessed by summarizing the incidence of treatment-emergent adverse events (TEAEs) and SAEs together with all other safety parameters.
7. Assessment of population-based PK parameters of lenvatinib.
8. Score changes from baseline for all PedsQL scales including Generic Core Scales and Cancer Module. Scores will be calculated for total generic score, total cancer score, each physical function subscale including physical health, psychosocial health, emotional function, social function, school/work function in the Generic Core Scales, and each subscale in the cancer module.
9. Palatability and acceptability of the suspension formulation of lenvatinib in subjects receiving the suspension formulation in the study will be assessed by using the Palatability Questionnaire (see Appendix 4 of the Protocol).

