**Table 3 OS Event and Censoring Method**

| Situation   | Date of Event or Censoring | Outcome |
|--|-----------------------------------|----------------|
| Death during study   | Date of death                     | OS Event       |
| Subject still alive at data cut-off (including death after data cut-off) | Date of data cut-off              | Censored       |
| Subject lost to follow-up or withdrawal of consent before data cut-off   | Date of last known to be alive    | Censored       |

OS = overall survival.

Overall survival (OS) will be compared between the treatment arm and control arm using the stratified log-rank test adjusted for the randomization stratification factor (refer to [Section 6.3.2](#)).

Median will be calculated using the K-M [[Kaplan and Meier, 1958](#)] product-limit estimates for each treatment arm along with 2-sided 95% CIs (estimated with a generalized Brookmeyer and Crowley method [[Brookmeyer and Crowley, 1982](#)]). The K-M estimates of OS will be plotted over time.

The Cox regression model will be used to estimate the hazard ratio and the corresponding 95% CIs stratified by the randomization stratification factor (refer to [Section 6.3.2](#)). For all

analyses using Cox regression, Efron's method will be used for handling "ties" in the failure time.

K-M estimates will also be presented for 4, 6, 9 and 12 months (ie, OS-1y) along with 2-sided 95% CIs (estimated with the Greenwood formula using the log-log transformation [[Greenwood \(1926\)](#) and [Kalbfleisch and Prentice \(2002\)](#)]). The OS-1y will be analyzed using the same approach as for the PFS-4m.

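### The SAP gives two overall survival (OS) censoring rules with different dates for subjects last confirmed alive before the cutoff, and Table 3 has no clear row for them

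*SAP*

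**What the plan says.** Section 6.1.2 (Secondary Endpoints) covers subjects lost to follow-up and subjects alive at the cutoff in one sentence. Both groups "will be censored at the date the subject was last known to be alive, or date of data cutoff for the primary analysis", whichever is earlier. Withdrawal of consent is not named.

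Section 6.4.2.2 (Overall Survival) splits these groups. For the first: "Subjects who were lost to follow-up or who withdrew consent will be censored at the date the subject was last known to be alive". For the second: "Subjects who are still alive at the data cut-off date will be censored at the data cut-off date".

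Table 3 follows Section 6.4.2.2. The row "Subject still alive at data cut-off (including death after data cut-off" is censored at the cutoff date. The row "Subject lost to follow-up or withdrawal of consent before data cut-off" is censored at the last-known-alive date. The only other row is death during the study.

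On the contact schedule, Section 4.2.2.2 says "Subjects in both Arm A and Arm B will be followed for survival every 12 weeks", with a one-week tolerance, and that follow-up "will continue for up to 2 years after end of treatment for a subject". Section 4.2.3.2 repeats both for the Extension Phase. Section 6.4 foresees a later OS analysis after the primary cutoff.

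**The concern.** For a subject who is neither lost nor withdrawn and was last confirmed alive before the cutoff, Section 6.1.2 gives the contact date and Table 3, read literally, gives the cutoff date or nothing. This is an ordinary situation. With contacts 12 weeks apart, most living subjects in survival follow-up will have had their last contact before the cutoff. A subject who has completed the 2-year follow-up has no further planned contact, yet was not lost and did not withdraw. Table 3 offers no row for that subject except the alive row, and the SAP does not say that survival must be confirmed at the cutoff.

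At stake are the OS log-rank test, the OS hazard ratio, the K-M curve and the OS-1y comparison. If a subject is credited with time during which a death would have gone unrecorded, OS is overstated. In an open-label trial the choice between two written rules should not be left to the time of analysis.

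**Working it through.** **The plan's own figure.** The SAP gives no OS assumption to reproduce. Its one sample-size figure is for PFS: 4 × (1.960 + 0.842)² / (ln 0.4)² = 31.4 / 0.840 = 37.4, rounded up to 38 events, as Section 5 states. It does not depend on the OS rule.

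**Where the rules agree and differ.**

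| Subject | Section 6.1.2 | Section 6.4.2.2 / Table 3 |
|---|---|---|
| Confirmed alive on or after cutoff | cutoff | cutoff |
| Lost to follow-up | last known alive | last known alive |
| Withdrew consent | not named | last known alive |
| Between contacts at cutoff | last known alive | no clear row; cutoff if treated as alive |
| Completed 2-year follow-up | last known alive | no clear row; cutoff if treated as alive |

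The gap in row 4 can reach 13 weeks, 13 × 7 / 30.4375 = 3.0 months. In row 5 it can be much longer. Suppose a subject is randomized at month 5, stops treatment at month 8 and has a final contact at month 32. At a month-44 cutoff, that subject is censored at 27 months by Section 6.1.2 and at 39 months if placed in the alive row.

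**Size of the effect.** Inputs from the SAP are 20-month accrual, primary cutoff at about month 32 (Section 5), 12-weekly contact and a cap at end of treatment plus 24 months. Assumptions of this review are exponential OS with medians of 10 to 20 months, treatment ending at month 3, and an illustrative later cutoff at month 44. The simulation used 400,000 subjects per scenario. Deaths are known only up to the last contact, and everyone else is placed in the alive row. Hazard is deaths divided by person-time, relative to the true rate. Contacts run every 12 weeks from end of treatment.

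| Cutoff | Assumed median | OS-1y: true → Table 3 | Median: true → Table 3 | Hazard understated |
|---|---|---|---|---|
| 32 | 10 | 0.436 → 0.438 | 10.0 → 10.0 | 5% |
| 32 | 14 | 0.551 → 0.553 | 14.0 → 14.2 | 6% |
| 32 | 20 | 0.660 → 0.662 | 20.0 → 20.9 | 7% |
| 44 | 10 | 0.436 → 0.436 | 10.0 → 10.0 | 12% |
| 44 | 14 | 0.552 → 0.552 | 14.0 → 14.0 | 16% |
| 44 | 20 | 0.660 → 0.660 | 20.1 → 20.1 | 19% |

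If the last contact instead falls at a random point in the 12 weeks before the cutoff, or exactly at the 2-year limit, the understatement is 4-5% at month 32 and 9-15% at month 44. In every scenario the Section 6.1.2 rule returned the hazard to within about 0.5%.

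The pattern follows from the follow-up times. The share of subjects whose 2-year limit has passed by the cutoff is (32 − 27)/20 = 25% at month 32 and (44 − 27)/20 = 85% at month 44, so the hazard error grows. By month 44 even the last subject enrolled has 44 − 20 = 24 months since randomization and a contact beyond 21 months, so OS-1y and a median up to 20 months are untouched.

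**The reverse case.** If all deaths up to the cutoff are known, for example from public records, the Table 3 rule is unbiased. Censoring survivors at last contact is then slightly pessimistic. At month 32, without the 2-year cap, a true median of 12 reads 11.9, 16 reads 15.6-15.7 and 20 reads 19.2-19.3 months.

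**The case against.** Table 3 does not say that unconfirmed subjects are credited with survival to the cutoff. Its row is for subjects still alive then, the parenthesis about later deaths presupposes information from beyond the cutoff, and lost or withdrawn subjects go to their last-known-alive date. Overstatement needs two further steps that the SAP does not write down: unconfirmed subjects are put in the alive row, and their deaths before the cutoff are not learned. This stands. A reader might infer that Table 3 overstates OS as written, but the text supports only a missing row and a conditional bias.

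The size is also modest where the plan places its analysis. A cutoff at month 24 would give a larger OS-1y error (0.461 against 0.435 for an assumed median of 10), but Section 5 expects about month 32, where the error is a few tenths of a point.

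A reader might further infer that the bias differs by arm, because chemotherapy stops after at most 5 cycles while lenvatinib in Arm A continues to progression. With identical survival and treatment assumed to end at month 9 in Arm A and month 3 in Arm B, the apparent A/B rate ratio is 1.00-1.02 at month 32 and 1.06-1.13 at month 44, against Arm A. But Section 4.2.4 lets Arm B subjects cross over to lenvatinib until next progression, and the SAP does not say whether that resets the follow-up clock. A difference is possible at late cutoffs; it is not established.

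Finally, OS is secondary and the primary PFS analysis is untouched. That limits the severity. It does not remove the contradiction.

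**Conclusion.** The SAP is wrong as written: it states two OS censoring rules that give different dates for ordinary subjects, and Table 3 leaves those subjects without a clear row. This should be fixed before the OS analysis.

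The numerical consequence is conditional on unconfirmed subjects being treated as alive and deaths since last contact not being ascertained. At the planned cutoff it is then small: OS-1y up to about 0.3 percentage points, the hazard understated by about 5-7%, and a true median of 20 months read as about 20.9. At a later OS cutoff such as month 44, the hazard is understated by about 12-19%. These figures rest on assumed exponential survival and treatment ending at month 3, and are somewhat lower under the alternative contact pattern shown.

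**What to change.** State one rule in Section 6.1.2, Section 6.4.2.2 and Table 3. Subjects not known to have died on or before the cutoff of the analysis in question are censored at the earlier of the last-known-alive date and that cutoff. The cutoff date then applies only when survival is confirmed on or after it. Name subjects who withdrew consent and subjects who completed the 2-year follow-up as falling under this rule. Refer to the cutoff of each analysis, because Section 6.1.2 now names only the primary one while Section 6.4 foresees a later OS analysis.

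The cost is one sentence in each section and one table row. OS estimates become slightly less favourable than with everyone credited to the cutoff, and slightly pessimistic if deaths are ascertained more completely than survival. A survival-status check of all subjects around each cutoff would reduce that residual effect.

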**Table 3 OS Event and Censoring Method**

| Situation   | Date of Event or Censoring | Outcome |
|--|-----------------------------------|----------------|
| Death during study   | Date of death                     | OS Event       |
| Subject still alive at data cut-off (including death after data cut-off) | Date of data cut-off              | Censored       |
| Subject lost to follow-up or withdrawal of consent before data cut-off   | Date of last known to be alive    | Censored       |

OS = overall survival.

Overall survival (OS) will be compared between the treatment arm and control arm using the stratified log-rank test adjusted for the randomization stratification factor (refer to [Section 6.3.2](#)).

Median will be calculated using the K-M [[Kaplan and Meier, 1958](#)] product-limit estimates for each treatment arm along with 2-sided 95% CIs (estimated with a generalized Brookmeyer and Crowley method [[Brookmeyer and Crowley, 1982](#)]). The K-M estimates of OS will be plotted over time.

The Cox regression model will be used to estimate the hazard ratio and the corresponding 95% CIs stratified by the randomization stratification factor (refer to [Section 6.3.2](#)). For all

analyses using Cox regression, Efron's method will be used for handling "ties" in the failure time.

K-M estimates will also be presented for 4, 6, 9 and 12 months (ie, OS-1y) along with 2-sided 95% CIs (estimated with the Greenwood formula using the log-log transformation [[Greenwood \(1926\)](#) and [Kalbfleisch and Prentice \(2002\)](#)]). The OS-1y will be analyzed using the same approach as for the PFS-4m.

#### 6.4.2.3 Overall Response Rate (ORR) and ORR-4m by IIR

The ORR by IIR is the proportion of subjects with a best overall response of CR or PR determined by IIR using RECIST 1.1. The ORR by IIR will be summarized and compared between the two treatment arms. The raw difference in ORR will be reported. The 2-sided 95% confidence interval of ORR difference will be generated from SAS using Miettinen-Nurminen (Score) Confidence Limits.

The ORR-4m by IIR will be summarized and compared between arms using the same approach as for ORR by IIR.

#### 6.4.2.4 Duration of Response, Disease Control Rate, and Clinical Benefit Rate by IIR

Median DOR by IIR among responders for each arm will be presented along with the corresponding 2-sided 95% CI; 95% CI will be estimated with the Brookmeyer and Crowley method.

Disease Control Rate (DCR) and CBR by IIR will be summarized and compared between arms using the same approach as for ORR.

#### 6.4.2.5 PFS, PFS-4m, PFS-1y, ORR-4m, ORR, DOR, DCR, and CBR by Investigator Assessment

Efficacy endpoints PFS, PFS-4m, PFS-1y, ORR-4m, ORR, DOR, DCR, and CBR evaluated based on investigator assessment will be analyzed using the same approach as for the endpoints assessed by IIR.

#### 6.4.2.6 Subjects Achieving Complete Resection

The difference in the proportion of subjects who achieve complete removal of baseline lesion(s) between the 2 treatment arms will be compared and corresponding two-sided 95% CIs will be calculated using the Clopper and Pearson method ([Clopper and Pearson, 1934](#)). The proportion of subjects with unresectable baseline lesions(s) that are converted to resectable lesions will be compared between the 2 treatment arms in the same way.

#### 6.4.2.7 Maximum Tumor Shrinkage

Graphical displays (waterfall plot) will be prepared for the maximum tumor shrinkage in target lesions, defined as the maximum percentage change from baseline in the sum of the diameters of the target lesions at data cutoff.

## **6.5 Pharmacokinetic, Pharmacodynamic, Pharmacogenomic, and Other Biomarker Analyses**

### **6.5.1 Pharmacokinetic Analyses**

Lenvatinib plasma concentration data will be summarized across timepoints using n, mean, SD, median, Q1, Q3, minimum, and maximum. Graphical displays will present scatter plots and box plots of lenvatinib plasma concentration over time. Plasma concentration of lenvatinib versus time data will be listed.

Plasma concentration data of lenvatinib will be analyzed using a population PK approach to estimate population PK parameters. The analysis will be detailed in a separate analysis plan.

### **6.5.2 Pharmacodynamic, Pharmacogenomic, and Other Biomarker Analyses**

Analyses related to PD, pharmacogenomics, and biomarkers will be detailed in separate analysis plans.

## **6.6 Safety Analyses**

All safety analyses will be performed on the Safety Analysis Set. Safety data, presented by treatment group, will be summarized on an “as treated” basis using descriptive statistics (eg, n, mean, standard deviation, median, minimum, maximum, Q1, and Q3 for continuous variables; n [%] for categorical variables), as appropriate. All safety data will be summarized up to the last dose + 30 days or the data cutoff date, whichever occurs earlier. Optional lenvatinib crossover treatment is permitted by protocol. For subjects in Arm B who crossed over to optional treatment with lenvatinib alone or lenvatinib plus chemotherapy, data records occurring on or after the date of the crossover (date of first administration of lenvatinib) will be excluded from this analysis. In addition, for these subjects, data occurring on or after the date of the crossover will be summarized and listed separately for selected parameters as appropriate.

Safety variables include TEAEs, clinical laboratory parameters, vital signs, 12-lead ECG results, Lansky play scores or Karnofsky performance scores, physical examination, height, tooth formation abnormalities, closure of proximal tibial plates, Tanner Stage, and left ventricular ejection fraction (LVEF). Study Day 1 for all safety analyses will be defined as the date of the first dose of study drug.

### **6.6.1 Extent of Exposure**

Extent of exposure to study treatment, study drug administered, and study drug modifications will be summarized and presented for each individual drug and overall as appropriate.

#### **6.6.1.1 Extent of Exposure of Study Drug**

Treatment duration and the total number of treatment cycles will be summarized descriptively. The maximum number of treatment cycles for each subject is the largest cycle

number in which a subject receives any non-zero dose of study drug(s). The number and percentage of subjects treated within each cycle will also be summarized for each treatment arm.

Treatment duration will be summarized descriptively for each individual drug and overall. The dosing end date for lenvatinib will be imputed to the analysis cutoff date if the subject is still on treatment at the time of the data cutoff, and the dose will be imputed with the last dose recorded in the database for that subject. However, the dosing end date/dose for chemotherapy (ifosfamide and etoposide) will be imputed as the last dose date/dose recorded in the database prior to or on the analysis cutoff date.

The duration of each individual drug in days will be calculated (as Date of the last non-zero dose – Date of the first non-zero dose + 1) for the specific drug, including drug interruption days. For overall treatment duration, it is defined as the duration between the earliest first dose start date of study drugs and the latest last dose end date of study drugs.

In this study, study drugs refer to any of the following: lenvatinib 14 mg/m^2, ifosfamide 3000 mg/m^2, and etoposide 100 mg/m^2.

#### 6.6.1.2 Study Drug Administration

The total dose received per subject, dose intensity, and relative dose intensity will be summarized with descriptive statistics for each individual study drug.

For each individual study drug, the total dose per subject (mg) will be calculated as the sum of all doses that subject has received during the study. The dose intensity (mg/m^2/day) will be calculated as the total dose (mg) received during the study divided by BSA on Cycle 1 Day 1 and the treatment duration of the specific drug (days). The relative dose intensity, which is defined as the ratio (%) of total dose received and total planned dose (ie, received dose as a percentage of planned dose), will be calculated as the dose intensity divided by the planned dose level.

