## 4.2 Overall Study Design and Plan

This is a multicenter, randomized, open-label, parallel-group, Phase 2 study to compare the efficacy and safety of lenvatinib in combination with ifosfamide and etoposide versus ifosfamide and etoposide in children, adolescents, and young adults with relapsed or refractory osteosarcoma.

Approximately 72 eligible subjects will be randomized to 1 of the following 2 treatment arms in a 1:1 ratio within the strata:

- Arm A: lenvatinib 14 mg/m^2 (orally, once daily) plus ifosfamide 3000 mg/m^2/day (intravenously [IV], Day 1 to Day 3 of each cycle for a total of up to 5 cycles) and etoposide 100 mg/m^2/day (IV, Day 1 to Day 3 of each cycle for a total of up to 5 cycles)
- Arm B: ifosfamide 3000 mg/m^2/day (IV, Day 1 to Day 3 of each cycle for a total of up to 5 cycles) and etoposide 100 mg/m^2/day (IV, Day 1 to Day 3 of each cycle for a total of up to 5 cycles)

Randomization will follow a predefined randomization scheme based on the following stratification factors: time to first relapse/refractory disease (early [ $<18$  months] or late [ $\geq 18$  months]) and age ( $<18$  and  $\geq 18$  years).

Eisai will closely monitor enrolment, to ensure that at least 36 subjects are  $<17$  years of age at the time of informed consent per regulatory requirement.

The study will be conducted in 3 Phases: a Prerandomization Phase, a Randomization Phase, and an Extension Phase.

The end of the study will be the date of data cutoff for the final analysis or the time of last subject last visit, whichever occurs later.

An overview of the study design is presented in Figure 1 in the Protocol.

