#### 4.2.2.1 Treatment Period

The Treatment Period for each subject will begin at the time of randomization and will end at the completion of the Off-Treatment Visit which will occur within 30 days after the final dose of study treatment.

Subjects will receive study treatment as continuous 21-day cycles in both treatment arms. Treatment cycles will be counted continuously regardless of dose interruptions. If chemotherapy administration is precluded on Day 1 of a treatment cycle, the subject may resume treatment once recovered at the discretion of the investigator. Subsequent chemotherapy will be administered every 21 ( $\pm 1$ ) days starting from the timepoint it was resumed. Subjects will undergo safety and efficacy assessments as defined in the Schedule of Procedures/Assessments (Table 5 of the Protocol). Subjects randomized to Arm A will continue to receive lenvatinib until disease progression (PD) confirmed by IIR, development of unacceptable toxicity, subject request, withdrawal of consent, or study termination by the sponsor, whichever occurs first.

Disease progression (PD) must be confirmed by IIR prior to the investigator discontinuing study treatment for a subject. In situations where the investigator judges that alternative treatments must be instituted immediately for a subject's safety, study drugs may be discontinued without waiting for IIR confirmation of radiographic evidence of PD. If possible, before discontinuation of the subject from the study, the investigator should consult with the sponsor.

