### 6.2.6 Treatment Compliance

Records of treatment compliance for each subject will be kept during the study, including the Follow-up Period. Clinical research associates will review treatment compliance during investigational site visits and at the completion of the study. Received dose as percent of planned dose per subject (ie, relative dose intensity) will be summarized as described in [Section 6.6.1.2](#); no other analysis of treatment compliance is planned.

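### Read literally, the relative dose intensity rule contradicts its own definition for ifosfamide and etoposide, giving 17.2% or 120.7% for five full on-schedule cycles

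*SAP*

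**What the plan says.** SAP Section 6.6.1.2 summarizes total dose, dose intensity and RDI for each study drug separately. Dose intensity, in mg/m²/day, is the total dose divided by Cycle 1 Day 1 BSA and by that drug's treatment duration in days. RDI is defined as the percentage of the planned total that was received, but the operational rule in the same sentence is that it "will be calculated as the dose intensity divided by the planned dose level".

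Section 6.6.1.1 sets each drug's duration as "Date of the last non-zero dose – Date of the first non-zero dose + 1", with interruption days counted. For chemotherapy it takes the last recorded dose date as the end date. It lists the study drugs as lenvatinib 14, ifosfamide 3000 and etoposide 100 mg/m².

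Section 4.2 gives both chemotherapy drugs on "Day 1 to Day 3 of each cycle for a total of up to 5 cycles", and Section 4.2.2.1 states that "Subjects will receive study treatment as continuous 21-day cycles in both treatment arms".

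Section 6.2.6 relies on this quantity for compliance: "Received dose as percent of planned dose per subject (ie, relative dose intensity) will be summarized as described in" Section 6.6.1.2. It adds that compliance will be analyzed in no other way.

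**The concern.** The calculation suits a drug taken every day, where calendar days and dosing days coincide. For a drug given on 3 days out of 21, the divisor in dose intensity includes about 18 undosed days for each completed cycle, while the only dose levels that the SAP lists for these drugs are amounts per dosing day. The result then cannot equal received over planned, which is how the same sentence defines RDI.

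This affects both study drugs in Arm B and two of the three in Arm A. Because the SAP names RDI as its sole compliance analysis, the chemotherapy compliance figures would be wrong. The error also depends on how many cycles a subject received, so a summary by arm would mix dose delivery with cycle count.

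**Working it through.** The SAP states no RDI value, so there is no figure to reproduce. The check applies its rule to a subject who receives every dose in full and on schedule.

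**Inputs**
- Daily dose d: ifosfamide 3000 mg/m², etoposide 100 mg/m² (Section 4.2)
- Dosing days per cycle: 3, for up to 5 cycles (Section 4.2)
- Cycle length: 21 days (Section 4.2.2.1)
- Duration: last minus first non-zero dose date, plus 1 (Section 6.6.1.1)
- Planned dose level: not defined for chemotherapy, so two readings are tried

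**Formulas for c cycles**
- Total dose = 3c × d
- Duration = 21(c − 1) + 3 days
- Dose intensity = 3c × d / [21(c − 1) + 3]
- Reading A, level = d: RDI = 3c / [21(c − 1) + 3]
- Reading B, level = 21-day average, 3d/21: RDI = 7 × the Reading A value

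The dose d cancels, so both chemotherapy drugs give the same results.

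| Full cycles | Dosing days | Calendar days | Reading A | Reading B |
|---|---|---|---|---|
| 1 | 3 | 3 | 100% | 700% |
| 2 | 6 | 24 | 25.0% | 175% |
| 3 | 9 | 45 | 20.0% | 140% |
| 4 | 12 | 66 | 18.2% | 127.3% |
| 5 | 15 | 87 | 17.2% | 120.7% |

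**Five cycles in full**
- Ifosfamide: 45000 / 87 = 517.2 mg/m²/day. Reading A: 517.2 / 3000 = 17.2%. Reading B: 517.2 / 428.6 = 120.7%.
- Etoposide: 1500 / 87 = 17.24 mg/m²/day. Reading A: 17.24 / 100 = 17.2%.
- By the SAP's own definition: 45000 / 45000 and 1500 / 1500, both 100%.

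Reading B fails because the duration stops at Day 3 of the last cycle and leaves out that cycle's remaining 18 days. With the last cycle counted in full, the duration is 5 × 21 = 105 days and Reading B gives (45000 / 105) / 428.6 = 100%.

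**Sensitivity to spacing (Reading A, five cycles).** Spacing of 20 days gives 15/83 = 18.1%, and 22 days gives 15/91 = 16.5%.

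**Ordering.** A subject given one cycle at half dose scores 1.5/3 = 50% under Reading A, above the 17.2% of a subject given all five cycles at full dose.

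**Lenvatinib.** With daily dosing for 105 days, (14 × 105 / 105) / 14 = 100%, so the formula is right for this drug.

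**The case against.** The strongest reply is that the planned dose level is undefined, and that the definition in the same sentence, which Section 6.2.6 repeats, is sound. A programmer who followed the definition would get sensible values, and Section 10 places derivation rules in separate documents. A reader might therefore infer from this point that 17% will appear in the study report. The SAP does not establish that. What stands is that its explicit calculation conflicts with its definition under either reading of the planned level, and unseen specifications cannot be assumed to override it.

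A reader might also infer that 100% is the only correct value after any number of full cycles. That holds if the planned dose counts cycles started. If it counts all five, full-dose subjects who stop after 1 to 4 cycles would score 20%, 40%, 60% and 80%. The SAP does not say which applies; only the five-cycle value is 100% either way.

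Finally, a reader might infer that the comparison of chemotherapy delivery between arms, and with it the interpretation of PFS, is invalid. The SAP does not support this. RDI is descriptive and enters no test, and the Per Protocol definition in Section 6.2.1 sets no RDI threshold. Sections 6.6.1.1 to 6.6.1.3 also report cycles received, subjects treated in each cycle, total dose and dose reductions by drug. The size of any distortion between arms is unknown, since it depends on each arm's cycle distribution. Most of the fall in Reading A comes between one and two cycles; from three to five cycles it is 20.0 − 17.2 = 2.8 percentage points.

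**Conclusion.** The point holds as an error in a stated derivation, confined to ifosfamide and etoposide. For five full on-schedule cycles the rule gives 17.2% or 120.7%, where the SAP's definition gives 100%. The discrepancy varies with cycle count, so it is not a constant factor that a reader could remove.

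This rests on Days 1 to 3 dosing, 21-day spacing and the duration formula as written. The two values reflect the two plausible meanings of the undefined planned level.

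The consequence is limited to a descriptive compliance and exposure statistic. PFS, the other efficacy analyses and the lenvatinib RDI are not affected. It should be fixed before the exposure tables are produced, but it does not threaten the trial's conclusions.

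**What to change.** In Section 6.6.1.2, restrict the present RDI formula to lenvatinib. For ifosfamide and etoposide:

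- Calculate RDI as cumulative mg/m² received divided by total planned mg/m², and state that the planned dose counts the chemotherapy cycles started.
- Report dose intensity per 21-day cycle, with duration running from the first dose to Day 1 of the last chemotherapy cycle, plus 21 days.

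Five on-schedule cycles then give RDI = 100% and, for ifosfamide, 45000 / 105 × 21 = 9000 mg/m² per 21 days, which equals the planned 3 × 3000.

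The downside is that RDI over cycles started does not itself show delays or early stopping. Delays appear in the dose intensity: if five full cycles were spaced 28 days apart, the duration would be 4 × 28 + 21 = 133 days and the ifosfamide dose intensity 45000 / 133 × 21 = 7105 mg/m² per 21 days, while RDI stayed at 100%. Early stopping appears in the cycle-count summaries, so the three should be presented together.

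The cost is a few sentences in the SAP and a revised chemotherapy derivation. No new data are needed, and no dose or schedule changes.
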